1. BACKGROUND

In 2014, according to the Centers for Disease Control and Prevention there were nearly 1.5 million new cancer cases diagnosed and almost 600,000 cancer-related deaths in the United States(1). In fact, cancer is the second leading cause of death in the United States; 1 in every 4 deaths is due to cancer. Novel therapies are much needed to improve the outcomes of cancer patients.

1.1 Immunotherapy Overview

Although the medical field has seen numerous discoveries none has been as revolutionary as that of immunotherapy, which harnesses the body's immune system to more effectively eliminate cancer cells. In fact, *Science* magazine named immunotherapy as the Breakthrough of the Year in 2013(2). Immune responses directed against tumor are one of the body's natural defenses against the growth and proliferation of cancer cells. However, over time and under pressure from immune attack, cancers develop strategies to evade immune-mediated killing allowing them to develop unchecked. One such mechanism involves upregulation of surface proteins that deliver inhibitory signals to cytotoxic T cells. Programmed cell death ligand 1 (PD-L1) is one such protein, and is upregulated in a broad range of cancers with a high frequency, with up to 88% expression in some tumor types. In a number of these cancers, including lung(3), renal(4), ovarian cancer(5), and hematologic malignancies(6) tumor cell expression of PD-L1 is associated with reduced survival and an unfavorable prognosis.

1.2 Immune Checkpoint Inhibitors

PD-L1 is part of a complex system of receptors and ligands that are involved in controlling T-cell activation. PD-L1 acts at multiple sites in the body to help regulate normal immune responses and is utilized by tumors to help evade detection and elimination by the host immune system tumor response. In the lymph nodes, PD-L1 on antigen-presenting cells binds to PD-1 or CD80 on activated T cells and delivers an inhibitory signal to the T cell(7). This results in reduced T cell activation and fewer activated T cells in circulation. In the tumor microenvironment, PD-L1 expressed on tumor cells binds to PD-1 and CD80 on activated T cells reaching the tumor. This delivers an inhibitory signal to those T cells, preventing them from killing target cancer cells and protecting the tumor from immune elimination(8).

The Food and Drug Administration (FDA) has recently approved several immunotherapy drugs called immune checkpoint inhibitors (ICIs) for treatment of lung cancer, bladder cancer, and several others based on clinical trials showing dramatic responses in patients that have progressed through standard treatments like chemotherapy(9, 10). These drugs decrease inhibitory signals, effectively "releasing the brake" on the immune system so that it may better identify and eliminate cancer cells.

Despite the improved outcomes with ICIs, clinical trials of ICI monotherapy show that only approximately 20% of patients will have a significant response. Combining an ICI with other therapies seems to be a more effective strategy and several trials have shown that giving multiple ICIs together results in improved outcomes although at the expense of increased toxicity(10-12).

1.3 Radiation Therapy and Immune Effects

The published literature consistently shows that RT can initiate and promote both innate and adaptive immunity against tumors by mechanisms including: 1) enhanced expression of damage

associated molecular patterns (DAMPs) leading to stimulation of dendritic cells and subsequent increase in antigen presentation; 2) enhanced expression of MHC class I molecules, adhesion molecules and stress-induced ligands, and death receptors on tumor cells leading to increased recognition and killing by T cells; 3) induction of chemokines CXCL9, CXCL10 and CXCL16 promoting recruitment of effector CD8+ T cells; and 4) release of pro-inflammatory cytokines such as interleukin 1 β , TNF α , IFN γ driving anti-tumor immunity(13-15). Because radiation therapy (RT) is a potent stimulator of the immune system and functions as an in situ tumor vaccine(13-15) by increasing tumor antigen presentation and T cell activation, preclinical studies have combined RT with an ICI that uniformly show that a robust synergism(14, 16).

Evidence of the potential for RT to generate antitumor immune responses has gained momentum in recent years. Lee et al. studied the effects of single fraction high dose RT on dendritic cells (DC) maturation and migration and noted that 5 days following a single fraction of 20 Gy, draining lymph nodes (LNs) showed an increase in tumor-specific DCs, which were associated with elevated markers of maturation(17). DCs from irradiated tissue are better able to stimulate effector T-cells, shown in mouse models of melanoma and breast cancer by Sharabi et al where hypofractionated RT of 18 Gy x 1 or 7 Gy x 3 increased the proliferation and activation of antigen specific CD8+ T-cells in the draining LNs compared to unirradiated controls(18). While limited preclinical data exist for the differential immune effects of fractionation(19), the impact of subsequent, delayed courses of radiotherapy has not been formally examined. The more dramatic implications of a systemic anti-tumor immune reaction are the occurrence of the socalled abscopal effect and an increased durability of response not seen with chemotherapy, suggesting the actions of a memory immune component.

There are not currently significant prospective data of RT and ICI combinations, although numerous clinical trials across many disease sites are currently either ongoing or planned. Many are hopeful that this treatment combination will improve outcomes based on anecdotal reports of RT causing tumor regression in lesions outside of the radiation field when given in addition to an ICI(20-22).

1.4 Rationale for Radiation Therapy and Immune Checkpoint Inhibitor Combination

Although RT is a localized treatment, directed at a specific anatomic target, it has very powerful systemic downstream effects including some that are immune system-related. First described in 1953, the term "abscopal effect" describes anti-tumor effects of RT that occur at a distant site outside of the treatment field(20). As such, RT has been described as an *in situ* tumor vaccine because it triggers a systemic anti-tumor response, in part by enhancing tumor neo-antigen exposure to antigen presenting cells (i.e. dendritic cells) that lead to robust T cell activation and migration to tumor(23, 24). These RT-induced effects may work in concert with those of systemic immunotherapy drugs, each with a unique mechanism of action. In fact, abundant preclinical data show dramatic synergy of RT given to one tumor with an ICI versus RT alone or ICI alone(16, 25, 26). For example, a group from Johns Hopkins University demonstrated in an intracranial glioma mouse model long-term survival only was achieved with combination ICI plus RT versus either ICI alone or RT alone (53 vs. 27 vs. 28 days; p<.05)(16).

In the absence of robust clinical data to inform whether RT plus ICI therapy should become more widely pursued in patients, a small but growing body of literature demonstrates that at least some patients do benefit from this combination. A recently published systematic review included 46 case reports of the abscopal effect identified from 1969 to 2014(27). Arguably the most well-known of these case reports described the abscopal effect in a melanoma patient who failed to

respond to an ICI alone, but after receiving palliative RT to a paraspinal mass had dramatic tumor regression in an unirradiated tumor(21). We highlight that our proposed clinical trial intends to utilize RT in a similar manner, being to stimulate a robust immune response in combination with an ICI in the setting of suboptimal response to ICI alone. Other studies also suggest that RT may be beneficial in addition to ICI therapy. A secondary analysis of the KEYNOTE-001 trial indicates that previous RT in patients with advanced lung cancer is associated with longer progression free survival and overall survival with pembrolizumab treatment (an ICI) compared to those who did not receive previous RT(28). A phase I study treating patients with metastatic melanoma or renal cell carcinoma with SBRT (20 Gy x 1-3 fractions) with concurrent IL-2 demonstrated a 68% (8 patients) complete (CR) or partial response (PR) rate with frequent abscopal responses among these patients(29).

1.5 Rationale for Radiation "Revaccination" Strategy with Immune Checkpoint Inhibitor

Although there is synergism between RT and ICIs, at least in the preclinical setting, it remains unclear what the "ideal" RT parameters are to maximize an immune response and consequently lead to tumor elimination.

One of these parameters is the number of tumors that receive RT, for which there is a complete lack of data. In fact, the dominant strategy used in both preclinical and clinical studies has been treating only one tumor with RT. We propose that treating multiple tumors with RT and ICI may lead to a more robust anti-tumor response. Because RT functions as an *in situ* tumor vaccine by exposing the immune system to novel tumor antigens the rationale to treat multiple lesions with RT is borrowed from that of infectious disease prophylaxis in which a single inoculation is intentionally followed by additional inoculations (or "booster shots") out over time. As such, it has been well described that the first exposure of a foreign antigen to the immune system leads to an initial antigen-specific response; subsequent exposure to the same antigen causes a more rapid and robust antigen-specific immune response(30).

Our group was the first to explore this concept in a preclinical study.(31) Mice bearing pancreatic tumors in three different sites (left flank, right flank, upper back) were injected with an ICI and exposed to 3 daily consecutive fractions of 4 Gy each to 1 versus 2 flank tumors (Figure 1).

Figure 1. Schematic representation of the treatment plan.(31) Three groups of mice were injected with mouse pancreatic cancer panc02 cells at three different sites: right flank (T1), left flank (T2), and the back (T3). Once the tumors reached ~50 mm³, mice in each group were injected with anti PD-L1 antibodies on day 1, 4 and 7. Group 1 received no further treatments while Groups 2 and 3 were irradiated (4 Gy) to the T1 tumor on Days 1, 2 and 3. Group 3 was subsequently irradiated (4 Gy) to the T2 tumor on Days 8, 9 and 10. Day 10 is considered day 0 of post end of treatment. Yellow circles indicate location of non-irradiated tumors. Red circles indicate location of irradiated tumors.

Chuong et al Fig. 1

Our data indicate that delivering an RT to a one flank followed by an RT "booster shot" to the contralateral flank tumor reduced tumor growth in the non-irradiated tumor in the upper back. RT-induced tumor regression in the non-irradiated site was observed earlier (day 9) in mice that received RT to two tumors compared to mice that received RT to a single tumor (day 17), demonstrating proof-of-principle that a "revaccinating" with radiation along with immunotherapy can lead to a more rapid immune response (Figure 2).

Figure 2. Evaluation of radiation booster shot in a mouse pancreatic cancer syngeneic model.(31) Panc02 cells were injected subcutaneously in the flanks of immunocompetent C57BL/6 mice and treated as indicated in Figure 1. Tumor volumes were measured by caliper at the indicated intervals and expressed as Tumor volume \pm standard error of the mean (SEM). Black line represents Group 1 (no RT), red line represents Group 2 (RT to the T1 tumor alone) and blue line represents Group 3 (RT to both T1 and T2 tumors). Measurements were performed on the T1 (A), T2 (B) and T3 (C) tumors of 8 mice up to 21 days post end of treatments. Insets: measurements performed on the initial 12 mice up to 11 days post end of treatments. Four mice per group were sacrificed on day 16 for blood, tumors and lymph nodes collections. * p<0.05, ** p<0.005 one-way ANOVA; * p<0.05 Student's paired t-test.

Chuong et al Fig. 2

Despite our data being the first to demonstrate that the number of tumors treated with RT influences tumor growth outside of the radiation field, we observed a modest and transient effect. There are several plausible reasons for this that have influenced the current trial design: 1) pancreatic cancer is not highly immunogenic(32) although the tumors included in this clinical trial are; 2) ICI was started concurrently with RT in the preclinical study although starting the ICI prior to RT has been suggested to be more effective(9) and therefore this sequence is included in the design of this clinical trial; 3) the radiation dose that we used in the preclinical study (4 Gy x 3) was possibly too low(9) to trigger a robust immune response and this has prompted a higher dose to be used in this clinical trial (8 Gy x 5, 6 Gy x 5).

Furthermore, we found that decreased growth of the non-irradiated tumor correlated with a transient increase of the CD4/CD8 T cell ratio in tumor and tumor associated macrophages in the draining lymph nodes (Figure 3). We are not aware of any other preclinical studies that have explored this same RT "revaccination" concept.

Figure 3: $CD4^+$ and $CD8^+$ T-cell subsets in the indicated mice tumors following indicated treatments.(31) CD4:CD8 ratios were determined for all tumors at sixteen (A-C) and twenty-two (D-F) days post end of treatment. Ratios are expressed ± standard error of the mean (SEM). Four mice per group were evaluated. ** p<0.005 one-way ANOVA;

* p<0.05 Student's paired t-test.

Chuong et al Fig. 3

To our knowledge there is only one published clinical report of multi-course RT and immunotherapy(33). Patients with metastatic cancer received 35 Gy in 10 fractions to 2 separate metastatic lesions with concurrent granulocyte-macrophage colony-stimulating factor (GM-CSF). Serious toxicities were uncommon. Immunomonitoring was not performed so the immunologic effect of the RT to the second tumor could not be specifically evaluated. Still, responses in non-irradiated tumors were observed in approximately 20% of patients. Note that this study was not performed with an ICI, and importantly that there are no existing prospective clinical trial data available to inform us about the probability of an abscopal response with ICI plus RT (whether to one or multiple lesions). There are numerous combination therapy trials ongoing that are targeting one lesion with RT but none that we know of that intentionally target multiple lesions.

Therefore, we propose a novel open label single arm phase 2 clinical trial to study the efficacy of RT given to 2 separate cancer lesions with concomitant ICI in generating an abscopal response within unirradiated tumor(s).

2. STUDY OBJECTIVES

Primary endpoint

• To evaluate best overall response rate (ORR) in non-irradiated lesion(s).

Secondary endpoints

- To evaluate ORR as defined by immune-related response criteria (irRC) in non-irradiated lesion(s).
- To evaluate duration of response (DOR) from the time CR or PR is first determined until the first date of documented progressive disease.
- To evaluate overall survival (OS) from the start of radiation therapy of the first lesion to the date of death for any cause.
- To evaluate progression free survival (PFS) from the start of radiation therapy of the first lesion to the date of progressive disease or death for any cause.
- To evaluate treatment-related adverse events.

3. STUDY DESIGN

This is an open label single arm phase 2 clinical trial in patients with metastatic solid malignancy of any histology who have previously experienced limited progression in at least 1 and up to 5 lesions while on ICI monotherapy.

All potential subjects are required to undergo screening evaluation to determine eligibility within 28 days of study enrollment.

As illustrated in the study schema (Figure 1), eligible subjects will continue the same ICI on which they experienced limited progression and will also receive radiation therapy (RT). RT for all subjects will consist of treating one tumor of the treating physician's preference (40 Gy in 5 fractions), and after a 1-week interval during which ICI is continued alone, RT will be given to a second and separate tumor (30 Gy in 5 fractions). No additional RT will be delivered. ICI will be continued until disease progression or unacceptable toxicity.

Diagnostic imaging studies will be performed to determine treatment response at baseline/screening, 8 weeks after initiation of RT to the first lesion and every 8 weeks thereafter.

A total of 52 subjects will be enrolled on this trial. The expected rate of accrual is 2 patients per month at a single institution over 26 months.

Figure 4. Study schema

4. SUBJECT SELECTION

Study subjects must fulfill all of the following inclusion and exclusion criteria to be eligible for enrollment on this study.

4.1 Inclusion Criteria

- 1. \geq 18 years of age at the time of study entry.
- 2. Eastern Cooperative Oncology Group (ECOG) performance status of 0, 1, or 2.
- 3. Life expectancy of \geq 12 weeks as estimated by the treating physician.
- 4. Metastatic carcinoma confirmed by biopsy or imaging study if biopsy is not deemed feasible.
- 5. Most recent anti-cancer therapy consists of a single ICI drug including but not limited to ipilimumab, nivolumab, pembrolizumab, atezolizumab.
- 6. Radiographic evidence of progression while on a single ICI drug in 1 and up to 5 lesions.
- 7. Eligible to continue ICI during and after radiation therapy.
- 8. ≥3 radiographically distinct and measurable lesions (primary and/or metastatic lesions) by RECIST 1.1 criteria, with ≥3 lesions separated from each other by ≥5 cm
- 9. Subjects must consent to all study procedures described in the protocol including radiographic evaluation and blood draws.
- 10. Immunosuppressive doses of systemic medication including steroids must be discontinued at least 14 days prior to the start of RT.
- 11. Adequate normal organ and marrow function as defined below:
 - a. Hemoglobin \ge 9.0 g/dL that may be achieved with transfusion
 - b. Absolute neutrophil count (ANC) $\geq 1.5 \times 10^{9}/L$ ($\geq 1500 \text{ per mm}^{3}$)
 - c. Platelet count $\ge 100 \times 10^{9}/L$ ($\ge 100,000 \text{ per mm}^{3}$)
 - d. Serum bilirubin \leq 1.5 x institutional upper limit of normal (ULN).
 - e. AST (SGOT)/ALT (SGPT) ≤ 2.5 x institutional upper limit of normal unless liver metastases are present, in which case it must be ≤ 5x ULN
 - f. Serum creatinine CL>40 mL/min by the Cockcroft-Gault formula (Cockcroft and Gault 1976) or by 24-hour urine collection for determination of creatinine clearance:

Males:

Females:

CreatinineCL=Weight (kg) x (140 - Age)x0.85(mL/min)72 x serum creatinine (mg/dL)
$$x$$
0.85

12. Female subjects must either be of non-reproductive potential (i.e., post-menopausal by history: ≥60 years old and no menses for ≥1 year without an alternative medical cause; OR history of hysterectomy, OR history of bilateral tubal ligation, OR history of bilateral oophorectomy), have a negative serum or urine pregnancy test within 14 days of study enrollment, and not be breastfeeding.

4.2 Exclusion Criteria

- 1. Any contraindication to having an MRI scan.
- 2. Chemotherapy, biologic agent, investigational therapy, or RT given within 14 days of study enrollment.
- 3. Symptomatic or uncontrolled brain metastasis requiring treatment.
- 4. The need for palliative RT to a non-target lesion prior to RT to one of 2 target lesion on this study.
- 5. Prior RT to any lesion that would receive RT on this protocol.
- 6. Prior RT to a lesion located within 4 cm of previously irradiated structures: spinal cord that previously received >45 Gy; brachial plexus that previously received >45 Gy; small/large intestine or stomach that previously received >45 Gy; prior total lung V20 >30%.
- 7. Prior RT that could lead to an unacceptably high risk of clinically significant normal tissue injury due to high cumulative normal tissue dose as determined by the investigator.
- 8. History of any primary malignancy with the exception of
 - a. Malignancy treated with curative intent and with no known active disease for at least 3 years before enrollment on this study.
 - b. Adequately treated non-melanoma skin cancer or lentigo maligna without evidence of disease.
 - c. Adequately treated carcinoma in situ without evidence of disease (i.e. cervical carcinoma in situ; superficial bladder cancer).
- Any unresolved toxicity (Common Terminology Criteria for Adverse Events version 5.0 > grade 2) from previous anti-cancer therapy. Subjects with irreversible toxicity that is not reasonably expected to worsen by treatment on this study are permitted to enroll on this study.
- 10. Active or prior documented autoimmune disease within the past 2 years. Subjects with vitiligo, type I diabetes mellitus, Graves disease, or psoriasis not requiring systemic treatment (within the past 2 years) are not excluded.
- 11. Subjects requiring systemic corticosteroid (>10 mg daily prednisone equivalent) or other immunosuppressive medication within 14 days of study enrollment.
- 12. Contraindication to IV contrast despite premedication for iodine allergy, which would limit the ability to assess radiographic response to study treatment.
- 13. Prior allogeneic organ transplantation.

- 14. Presence of liver cirrhosis.
- 15. Active or prior documented inflammatory bowel disease (i.e. Crohn's disease, ulcerative colitis).
- 16. History of leptomeningeal metastases.
- 17. Any condition in the opinion of the investigator that would interfere with evaluation of study treatment or interpretation of patient safety or study results.
- 18. History of intolerance to any immune checkpoint inhibitor.
- 19. Female patients who are pregnant or breastfeeding.

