5.1 Immune Checkpoint Inhibitor

Subjects will continue to receive the same ICI that was previously administered at the time of documented progression at a standard schedule and dosage.

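### Exclusion 2 bars any biologic agent in the 14 days before enrolment and does not exempt the checkpoint inhibitor that defines the trial population

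*Combined protocol and SAP*

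**What the plan says.** Section 4 makes every criterion binding: "Study subjects must fulfill all of the following inclusion and exclusion criteria to be eligible for enrollment on this study". Exclusion 2 in section 4.2 then excludes patients with "Chemotherapy, biologic agent, investigational therapy, or RT given within 14 days of study enrollment". It carries no qualification, and the protocol does not define a biologic agent anywhere.

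The population is defined by current ICI treatment. Section 4.1 asks for "Most recent anti-cancer therapy consists of a single ICI drug" (item 5, which names ipilimumab, nivolumab, pembrolizumab and atezolizumab as examples) and for "Radiographic evidence of progression while on a single ICI drug in 1 and up to 5 lesions" (item 6). Item 7 requires that the patient can stay on the ICI during and after radiation. Section 3 says that "eligible subjects will continue the same ICI on which they experienced limited progression", and section 5.1 that "Subjects will continue to receive the same ICI that was previously administered at the time of documented progression at a standard schedule and dosage".

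Two timing instructions also bear on this. Section 5.2 asks for the first radiation fraction (Day 1) no later than 10 calendar days after enrolment. Section 5.3, item 7, asks that radiation to the first lesion start no more than 14 days after the preceding ICI dose. Both are worded as what should happen, not as eligibility rules.

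**The concern.** The design takes patients straight from ICI monotherapy and keeps them on it. The drug most likely to have been given in the 14 days before enrolment is therefore the qualifying ICI itself, and Exclusion 2 as written counts that dose against the patient.

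Staff who apply the text literally would turn away or delay the patients the trial is for. Staff who apply the probable intent would be departing from a criterion that section 4 makes mandatory, and each such enrolment could be recorded as an eligibility deviation. Delay also runs against sections 5.5 and 5.12, which urge a quick start to radiation because these patients have progressive disease.

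**Working it through.** The plan states no figure on this point, so there is none to reproduce. The check is a reading of the text followed by a count of days.

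**Is the ICI a biologic agent?** The protocol never says so in those words. The four drugs named in section 4.1, item 5, are antibodies, and section 1.5 describes the ICI in the sponsor's own animal work the same way: "mice in each group were injected with anti PD-L1 antibodies on day 1, 4 and 7". In ordinary usage a therapeutic antibody is a biologic.

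**Is there an exemption elsewhere?** No. Other exclusions do state exceptions: Exclusion 8 opens with "History of any primary malignancy with the exception of", the item on unresolved toxicity admits patients with irreversible toxicity that is not expected to worsen, and Exclusion 10 lists autoimmune conditions that remain acceptable.

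**Inputs**
- Washout: 14 days (Exclusion 2).
- Enrolment to Day 1: g = 0 to 10 days (section 5.2).
- ICI dose to first radiation: at most 14 days (section 5.3, item 7).
- Dosing interval T: not in the document. T = 14, 21, 28 and 42 days are assumptions.
- d = days since the last ICI dose at enrolment, from 1 to T, with dosing on schedule. On day T the next dose is due and is given after enrolment.

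**Exclusion 2 alone.** It passes if d > 14, which leaves T − 14 days: 0, 7, 14 and 28. If exactly day 14 is allowed, one day is added.

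**Exclusion 2 with sections 5.2 and 5.3, item 7.**
- If no dose falls between enrolment and Day 1, the gap from dose to radiation is d + g. With d > 14 this always exceeds 14, so the two rules cannot both be met. If day 14 is allowed, the one exception is d = 14 with g = 0.
- If the next dose falls in that window, then d + g ≥ T. The gap is d + g − T, which is at most 10, so section 5.3 is met. With g ≤ 10 this needs d ≥ T − 10.
- Both rules can therefore be met from day max(15, T − 10) to day T. For T = 21 that is days 15–21 (7 days), for T = 28 days 18–28 (11) and for T = 42 days 32–42 (11). For T = 14 there are none.

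**With the ICI exempted.** Either d ≤ 14 with prompt radiation, or d ≥ T − 10 with a dose before Day 1, is enough. For T = 14 and T = 21 these two ranges cover the whole cycle. For T = 28 and T = 42 they give 14 + 11 = 25 days.

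| Assumed T (days) | Days passing Exclusion 2 | Days also able to meet 5.2 and 5.3(7) | Days able to meet 5.2 and 5.3(7) with the ICI exempted |
|---|---|---|---|
| 14 | 0 (1) | 0 (1) | 14 |
| 21 | 7 (8) | 7 (8) | 21 |
| 28 | 14 (15) | 11 (12) | 25 |
| 42 | 28 (29) | 11 (12) | 25 |

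Parentheses: exactly day 14 allowed.

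The counts depend slightly on how days are numbered. If the cycle runs from 0 (dose day) to T − 1, the strict counts are 0, 6, 13 and 27 in the second column and 0, 6, 10 and 10 in the third.

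**The case against.** The strongest reply is that there is no strict contradiction. Inclusions 5 to 7 do not require a dose in the 14 days before enrolment, and section 5.1 governs what happens once the patient is a subject. A patient on a longer interval, or with a late dose, can enrol after day 14, receive the next dose and start radiation within 10 days. This stands: outright exclusion arises only under an assumed 14-day interval with dosing on schedule. In the other cases the rule restricts dates.

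It can also be said that the intent is plain, because section 5.3, item 7, presupposes recent ICI dosing, and that exceptions elsewhere in the list prove little about silence here. The likely intent is granted. But a mandatory criterion is checked against its wording, and nothing in the wording limits it to other agents.

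A third argument is that Exclusion 2 also lists radiation, yet nobody reads it as barring the study's own radiation, so the ICI deserves the same contextual reading. The parallel fails. The criterion concerns treatment already given when the patient enrols. Study radiation comes afterwards, whereas the qualifying ICI has been given beforehand.

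Finally, the protocol never calls an ICI a biologic agent, and the passage in section 1.5 concerns a mouse reagent. That is correct, but few readers would classify a therapeutic antibody otherwise.

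**Conclusion.** The concern holds as a minor error of wording. As written, a binding exclusion catches the treatment that defines the trial population and so misstates who may enrol and when. The conclusion rests on the ordinary meaning of biologic agent and on the absence of any exemption. The day counts rest additionally on assumed dosing intervals and on-schedule dosing. They describe how tightly the rule limits enrolment dates and do not estimate patients lost. The document does not show that anyone was turned away. Nothing in the Simon two-stage design or the analysis of the primary endpoint changes.

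**What to change.** In Exclusion 2, insert the words (other than the qualifying ICI) directly after the reference to a biologic agent. The washout then applies to every other agent, as was probably meant. Sections 5.2 and 5.3, item 7, can stay as they are, because with the exemption they can be met together at each interval considered. The cost is one clause in an eligibility amendment, with no change to sample size, design or analysis.
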